### *Phase 2*

Once the Safety Lead-in is completed and the proposed dose combination and schedule (including ramp-up) is confirmed safe and tolerable, additional patients will be enrolled and treated for the Phase 2 response evaluation. The Phase 2 portion will utilize a Simon's two-stage optimal design. Patients enrolled during the Safety Lead-in will be included in the Phase 2 portion of the study if they are evaluable for response. In the absence of study holds to accrual for toxicity or for futility, accrual will continue until 18 evaluable participants are treated at the tolerated dose and schedule.

An early stopping rule for futility will be based on the response rate in the first 7 patients. Accrual may need to be temporarily held at 7 patients pending response evaluation.

### *TLS Prophylaxis and Monitoring*

To mitigate the risk for TLS, all participants will initiate TLS prophylaxis and undergo pre-dose and real-time post-dose monitoring during the ramp-up stage (see [Section 5.10.2](#)). Patients will be monitored for TLS on an outpatient basis for the first 8 days of treatment.

### *Response*

PTCL specific response assessment criteria per Lugano Classification will be used for this study [50]; these criteria incorporate PET for response assessment. PTCL is considered [F] fluorodeoxyglucose (FDG) avid [51, 52] and PET-CT is recommended for staging of routinely FDG-avid histologies [50]. CT is preferred for low or variable FDG avidity.

Radiographic imaging will occur every 2 cycles. Ending treatment due to disease progression will occur after completing at least two cycles of treatment. This is to ensure that participants have had enough time to be exposed to the steady-state venetoclax dose.

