## Study Design

This is an open-label multi-site Phase 2 study with a Safety Lead-in to test the safety and efficacy of venetoclax with romidepsin for the treatment mature T-cell lymphoma.

During the safety-lead in, 6 evaluable participants will be enrolled using a 3+3 design. A Simon 2-stage optimal design will be utilized for the Phase 2 portion of the trial. Participants enrolled during the Safety Lead-in will be included in the Phase 2 portion of the study if they are evaluable for response. In the absence of study holds to accrual for toxicity or for futility, accrual will continue until 18 evaluable participants are treated.

PTCL patients will be treated with up to 26 cycles with venetoclax and romidepsin. Treatment cycles will be 28-days.

Participants will continue with treatment until disease progression, unacceptable toxicity or completion of 26 cycles of protocol therapy, whichever comes first.

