### *Treatment program*

Participants will receive venetoclax once daily orally, and romidepsin once a week for the first three weeks of each 28-days treatment cycle. Prior data suggest that B-cell NHL patients can tolerate up to 1200 mg/day venetoclax [15, 32]. However, due to biologic differences in T cell and B cell lymphomas and aggressive nature of T-cell disease, a maximum dose of 800 mg/day will be tested in this study. Romidepsin dosing will be according to the label.

On-target effect of either romidepsin or venetoclax could lead to rapid cell death and pose a risk of TLS. Based on prior clinical experience with the agent, a ramp up dosing schedule will be implemented during Cycle 1. The venetoclax dose will be ramped up over 7 days, in line with current practice for AML [30].

Once the safety and tolerability of the proposed dose combination and schedule is established after the safety lead-in, additional patients will be enrolled and treated for the Phase 2 response evaluation using the same dose combination and schedule (which includes the ramp-up in Cycle 1).

Participants will continue with treatment until disease progression, unacceptable toxicity or completion of 26 cycles (~24 months) of therapy, whichever comes first. If a patient is still benefiting from treatment at the completion of 26 cycles of therapy, we will consider amending the study to extend the duration of therapy for that particular patient.

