### *Dose and Schedule:*

During Cycle 1, participants will take venetoclax 20 mg/day on Day 1, 50 mg/day on Day 2, 100 mg/day on Day 3, 200 mg/day on Day 4, 400 mg/day on Day 5, and 800 mg/day on Days 6-7 in the ramp-up phase and 800 mg/day on Days 8-28. Romidepsin 14 mg/m^2 will be administered on Days 1, 8, and 15 of the 28-day cycle.

During Cycle 2+, participants will take 800 mg/day venetoclax. Romidepsin 14 mg/m^2 will be administered on Days 1, 8, and 15 of each 28-day cycle.

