#### **5.1 Treatment Program Overview**

This is a multi-center, open-label, single-arm Phase 2 trial of venetoclax with romidepsin for patients with relapsed/refractory mature T-cell lymphoma.

The study consists of a Safety Lead-in stage to evaluate safety/tolerability and a Phase 2 stage to evaluate anti-tumor activity in the study population ([Section 5.3](#)). Participants will receive up to 26 cycles of therapy and each cycle will be 28 days.

Protocol treatment will continue until disease progression, unacceptable toxicities, completing 26 cycles of therapy, or meeting other [Section 5.7](#) criteria, whichever comes first. If a patient is still benefiting from treatment at the completion of 26 cycles of therapy, we will consider amending the study to extend the duration of therapy for that particular patient.

During Cycle 1, all participants will be monitored closely for tumor lysis syndrome (TLS, [Section 5.9.2](#)).

Participants who discontinue protocol therapy will undergo follow-up (see [Section 5.8](#)). Windows for all assessments and treatments are detailed in [Section 10.0](#).

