#### **5.6 Duration of Therapy and Criteria for Removal from Protocol Therapy**

Participants will receive protocol therapy until one of the below criteria are met:

- Disease progression
- Completed 26 cycles (~24 months) of protocol therapy
- Participant is deemed intolerant to protocol therapy because of toxicity, despite dose modification/ delay
- General or specific changes in the patient's condition which render the patient unacceptable for further treatment in the judgment of the investigator
- Withdrawal of consent for further protocol therapy (see [Section 16.5](#))

Once participants meet criteria for removal from protocol therapy, the participant should then proceed to End of Treatment assessments. If a patient is still benefiting from treatment at the completion of 26 cycles of therapy, we will consider amending the study to extend the duration of therapy for that particular patient.

Documentation of the reason for discontinuing protocol therapy and the date effective should be made in the source documentation and appropriate eCRF. The COH DCC should be promptly notified of the change in participant status.

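### Section 2.7 requires two cycles before treatment stops for progression; the synopsis, 5.1, 5.6 and the calendar stop at progression with no minimum, and nothing says which governs

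*Combined protocol and SAP*

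**What the plan says.** The Response paragraph of Section 2.7 states: "Ending treatment due to disease progression will occur after completing at least two cycles of treatment". It gives the reason: "This is to ensure that participants have had enough time to be exposed to the steady-state venetoclax dose".

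Elsewhere the rule has no minimum:

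- Synopsis, Study Design: "Participants will continue with treatment until disease progression, unacceptable toxicity or completion of 26 cycles of protocol therapy, whichever comes first".
- Section 2.7, Treatment program: "Participants will continue with treatment until disease progression, unacceptable toxicity or completion of 26 cycles".
- Section 5.1: "Protocol treatment will continue until disease progression, unacceptable toxicities, completing 26 cycles of therapy".
- Section 5.6: "Participants will receive protocol therapy until one of the below criteria are met". Progression is the first criterion listed. Others are intolerance, withdrawal of consent, and changes in the patient's condition "which render the patient unacceptable for further treatment in the judgment of the investigator".
- Table 10.0, footnote b: therapy runs to unacceptable toxicity or progression, up to 26 cycles.

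Section 12.3 takes for granted that some patients stop for progression before two cycles, and counts them as evaluable non-responders. Footnote y of Table 10.0 puts the first scheduled disease assessment at Cycle 3 Day 1, with a window of 7 days before and none after.

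**The concern.** A patient who progresses in Cycle 1 or 2 gets opposite instructions from the same protocol. Under the Response paragraph of 2.7, progression is not yet a reason to stop. Under 5.6 it is. The trial is multi-site, so two investigators could treat the same situation differently and each cite the protocol.

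What is at stake is continued exposure to two active drugs after they have failed in that patient, and a delay in moving to other treatment. The 2.7 paragraph itself makes no allowance for a patient who is deteriorating. The population has relapsed or refractory disease after at least two systemic therapies (Section 3.1), and 2.7 itself describes the disease as aggressive, so early progression is a foreseeable event.

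**Working it through.** **1. The texts side by side, for a patient whose progression is found before the end of Cycle 2**

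| Place | Stop for progression now? |
|---|---|
| 2.7, Response | No, not until two cycles are complete |
| Synopsis, Study Design | Yes |
| 2.7, Treatment program | Yes |
| 5.1 | Yes |
| 5.6 | Yes |
| Table 10.0, footnote b | Yes |
| 12.3 | Assumes that some patients do |

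Section 2.7 disagrees with itself, and no order of precedence is given.

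**2. When the conflict can arise**

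Cycles last 28 days, so Cycle 3 Day 1 is study Day 2 × 28 + 1 = 57. The 7-day window opens on Day 57 − 7 = 50. A first scheduled scan on Days 50-56 falls inside Cycle 2, and progression seen on it comes before two cycles are complete. A scan on Day 57 raises no conflict. Progression detected before Day 50 would have to be clinical or come from an unscheduled scan.

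**3. Extra planned treatment from the earliest scheduled scan (Day 50)**

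The inputs are the dose schedule in 2.7 (20, 50, 100, 200 and 400 mg on Days 1-5, then "800 mg/day on Days 6-7 in the ramp-up phase and 800 mg/day on Days 8-28", and 800 mg daily in Cycle 2) and romidepsin on Days 1, 8 and 15 of each cycle. The calculation assumes full dosing without holds, and progression found before that day's dose.

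- Cycle 1 venetoclax: 20 + 50 + 100 + 200 + 400 + 23 × 800 = 19,170 mg.
- Cycle 2 venetoclax: 28 × 800 = 22,400 mg.
- Two-cycle total: 41,570 mg.
- Remaining on Days 50-56: 7 × 800 = 5,600 mg, and 5,600 / 41,570 = 13.5%.
- Cycle 2 romidepsin falls on Days 29, 36 and 43. Even with the +3-day window on the last infusion (Day 46), none remains after Day 50.

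**4. The reason given for the minimum**

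The 800 mg dose starts on Day 6. By the end of Cycle 1 a patient on schedule has had 23 days at that dose, and by Day 56 has had 56 − 5 = 51 days. Two full cycles therefore go well beyond reaching the target dose.

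**5. The design's error rates**

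Section 12.1.2 specifies 7 evaluable patients in stage 1 (stop at 0 responses), 18 in total, and rejection at 4 or more responses. With true response rate p,

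P(reject) = Σ over x = 1 to 7 of C(7,x) p^x (1−p)^(7−x) × P(Bin(11, p) ≥ 4 − x).

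- p = 0.10: 0.0893, within the stated 10%.
- p = 0.30: 0.8000, matching the stated 80%.

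The plan's design reproduces. These figures depend on who is in the denominator. Under 12.3 a patient who stops early for progression stays in as a non-responder. A patient kept on to two cycles is assessed at that point and also stays in. Either resolution leaves both figures where they are.

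**6. PFS**

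Table 11.3 dates progression at the day the criteria are first met, whether or not treatment continues. The PFS date is the same under either rule.

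**The case against.** The strongest reply is that 2.7 is a rationale section inside Background, while 5.6 is the section that sets out the criteria for removal. A site deciding whether to stop would turn to 5.6 and the calendar, which agree with each other and with 12.3. The two-cycle sentence also directly follows the statement that imaging is done every two cycles, so it may only describe when progression will normally be seen. And 2.7 restricts stopping for progression alone: a deteriorating patient can still come off for intolerance, by investigator judgment or by withdrawing consent.

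Much of this stands. It narrows the practical conflict to clinical or unscheduled findings and to a scan in the last week of Cycle 2, and it means no patient is locked into treatment. It does not remove the conflict. The sentence is worded as a rule and is justified by drug exposure, not by scan timing. The protocol does not rank its sections. The other exits in 5.6 are ways round the rule and do not say what to do about progression itself.

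A reader might go further and infer that early progressors could be removed on investigator judgment, treated as stopping for other reasons under 12.3, and replaced, which would raise the type I error. The documents do not support this. Section 12.3 classifies by cause, and a stop caused by progression is already counted as a non-response. They also give no basis for how often a misclassification would happen.

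**Conclusion.** The text is wrong as written, and the severity is low. Section 2.7 contradicts five other statements of the stopping rule and the assumption in 12.3. The consequence concerns patient management and safety. Type I error (0.089), power (0.800) and the PFS date do not change, provided 12.3 is applied as it stands.

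In the one scheduled situation where the rules diverge, the difference is at most 7 venetoclax doses (5,600 mg) and no romidepsin. A reader might infer a much larger excess: progression on Day 15, for example, would leave 42 × 800 = 33,600 mg (80.8% of the two-cycle total) and 4 infusions. That arithmetic is right for a patient on full dose, but no scan is scheduled then, and the documents do not say how often progression is found that early. It shows what could happen to an individual patient and is not a measure of the expected effect.

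**What to change.** Delete the two-cycle sentence from the Response paragraph of 2.7, together with the sentence giving its reason, which has no meaning alone. Section 5.6 then governs, consistent with the synopsis, 5.1, the calendar and 12.3. No change is needed to 12.3, the sample size or the decision boundaries.

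The cost is a small text edit and the loss of the stated aim of steady-state exposure before a progression stop. That loss is small, since the target dose is reached on Day 6. Keeping the minimum instead would mean writing it into 5.6 and aligning the other four places that stop at progression, as well as 12.3.

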### *Correlative studies*

Baseline and optional tumor tissue samples during Cycle 1 or 2 treatment will be collected. Correlative studies will characterize the gene expression profile in patient samples and explore relevance to the Bcl-2 pathway. Additionally, these studies will explore response to therapy and toxicity based on the patient's BCL-2 status.

### 3.0 ELIGIBILITY CRITERIA

Patient MRN

Patient Initials (F, M, L):

Participants must meet all of the following criteria on screening examination to be eligible to participate in the study:

#### 3.1 Inclusion Criteria

Informed Consent and Willingness to Participate

- 1. Documented informed consent of the participant and/or the legally authorized representative
- 2. Be willing to provide tissue (See [Section 9.1](#))

Age and Performance Criteria

- 3. Age  $\geq$  18 years
- 4. ECOG  $\leq$  2

Nature of Illness and Treatment History

- 5. Resolution of all acute toxic effects of prior therapy or surgical procedures to CTCAE Grade  $\leq$  1 (except alopecia).
- 6. Failed at least 2 prior systemic therapies. For ALCL histologies this must include failure or intolerable side effects of brentuximab vedotin
- 7. Histologically confirmed PTCL as defined by the WHO criteria 2016, excluding CTCL. Transformed mycosis fungoïdes is allowed.
- 8. Measurable disease defined as:
  - CT/MRI/ or PET scan, with at least one nodal site of disease which is 1.5 cm in longest dimension, and/or spleen  $>$  13 cm in vertical length, and/or diffuse enlargement of liver with or without focal nodules (Lugano 2014). Extra nodal sites with biopsy proven abnormal lesions are allowed including skin.
  - Patients with only bone marrow involvement will be acceptable.
- 9. Prior stem cell transplant allowed
  - If allogeneic HCT must have recovered from acute toxicity
  - Cannot have active acute or chronic GvHD and must be off immunosuppressive therapies

Clinical Laboratory Criteria (To be performed within 14 days prior to Day 1 of protocol therapy)

 10. ANC $\geq$ 1,000/mm  NOTE: Growth factor is not permitted within 7 days of ANC assessment unless cytopenia is secondary to disease involvement. Exception: Unless documented bone marrow involvement by lymphoma	ANC:	Date:
 11. Platelets $\geq$ 30,000/mm  NOTE: Platelet transfusions are not permitted within 7 days of platelet assessment unless cytopenia is secondary to disease involvement. Exception: Unless documented bone marrow involvement by lymphoma	Plts:	Date:

12. Total bilirubin $\leq 1.5 \times$ ULN ( $\leq 3 \times$ ULN for Gilbert's Syndrome or documented hepatic involvement by lymphoma)	ULN: Bil:	Date:
13. AST $\leq 3 \times$ ULN If hepatic involvement by lymphoma: AST $\leq 5 \times$ ULN	ULN: AST:	Date:
14. ALT $\leq 3 \times$ ULN If hepatic involvement by lymphoma: ALT $\leq 5 \times$ ULN	ULN: ALT:	Date:
15. Creatinine clearance of $\geq 50$ mL/min per 24 hour urine or the Cockcroft-Gault formula  $\text{CrCl} \text{ (mL/min)} = \frac{(140-\text{age}) \times \text{actual body weight (kg)}}{72 \times \text{serum creatinine (mg/dL)}} \text{ (} \times 0.85 \text{ for females)}$ 
Or
 $\text{CrCl} \text{ (mL/min)} = \frac{(140-\text{age}) \times \text{actual body weight (kg)}}{0.8136 \times \text{serum creatinine (umol/L)}} \text{ (} \times 0.85 \text{ for females)}$	Serum Cr:  Cr Clearance:	Date:
16. Women of childbearing potential (WOCBP): negative urine or serum pregnancy test If the urine test is positive or cannot be confirmed as negative, a serum pregnancy test will be required	Urine:  Serum:	Date:

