- r. *Adverse event (AE)* will be assessed using CTCAE v.5.0. SAEs related to study procedures will be recorded and reported from time of informed consent until Day 1 of protocol therapy.
- s. Toxicities AE recording and reporting will continue until the completion of [Safety Follow-up period](#) or until resolution or stabilization of any reportable AE occurring during Safety Follow-up.
- t. *Women of child bearing potential*: Pregnancy serum or urine test.
- u. *Screening laboratory assessments* to be performed within 14 days prior to start of protocol therapy.
- v. *Serum chemistry* panel to include: glucose, Blood Urea Nitrogen (BUN), creatinine, uric acid, total protein, albumin, magnesium, bicarbonate, calcium, inorganic phosphorous, sodium, potassium, chloride, total CO2, total bilirubin, alkaline phosphatase, ALT, AST, and LDH.
- w. *TLS serum chemistry monitoring post-Day 1, Day 2, Day 3, Day 4, Day 5, Day 6, Day 7 and Day 8 dose* to include potassium, uric acid, phosphorus, calcium, and creatinine. **Monitoring times are:** predose, and post dose 6-8 hours

and 24 (+/- 2) hours. Next dose should not be administered until 24 h blood chemistry values are evaluated. See **Table 5.9.1.**

- x. CT/MRI imaging for PTCL at baseline.
- y. *Disease and response assessment:* Cycle 3 Day 1 (-7 days), then every 2 cycles (-7 days). CT scan may take place within 7 days prior to D1 but not after D1 of the cycle in question.
- z. FDG-PET scan will be performed at screening. Subsequent PET scans will not be needed until the EOT visit or disease progression, whichever comes first.
- aa. *Bone marrow biopsy/aspirate* that was performed within 120 days prior to Day 1 may serve as Screening assessment.
- bb. PTCL response (Lugano criteria). Refer to [Section 11.3](#) for details.
- cc. *TLS prophylaxis* to be initiated prior to protocol therapy within 72 hours as stated in [Table 5.9.1](#). Participants should receive continued TLS prophylaxis as clinically indicated.
- dd. Refer to [Section 5.3](#) for the treatment plan. Refer to [Section 6.2](#) for dose modification/ delay guidelines and [Section 5.9](#) for supportive care guidelines.
- ee. Romidepsin will be administered intravenously on Days 1, 8, and 15 of each cycle. A window is allowed for romidepsin infusion visits (within  $\pm 3$  days of day 1 and within +3 days of days 8 and 15)
- ff. *Pill Diary* will be given to the participant and will be reviewed for adherence. See [Appendix G](#).

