**Disease Parameters**

- Measurable disease

Measurable lesions are defined as those that can be accurately measured in at least one dimension (longest diameter to be recorded) as  $\geq 15$  mm ( $\geq 1.5$  cm) by chest x-ray, CT scan, MRI, or calipers by clinical exam. All tumor measurements must be recorded in millimeters (or decimal fractions of centimeters).

Note: Tumor lesions that are situated in a previously irradiated area might or might not be considered measurable

- Malignant lymph nodes

To be considered pathologically enlarged and measurable, a lymph node must be  $\geq 15$  mm ( $\geq 1.5$  cm) in short axis when assessed by CT scan (CT scan slice thickness recommended to be no greater than 5 mm [0.5 cm]). At baseline and in follow-up, only the short axis will be measured and followed.

- Non-measurable disease

Pathological lymph nodes with  $\geq 10$  to  $<15$  mm [ $\geq 1$  to  $<1.5$  cm] short axis), are considered non-measurable disease. Bone lesions, leptomeningeal disease, ascites, pleural/pericardial effusions, lymphangitis cutis/pulmonitis, inflammatory breast disease, and abdominal masses (not followed by CT or MRI), are considered as non-measurable.

- Note: Cystic lesions that meet the criteria for radiographically defined simple cysts should not be considered as malignant lesions (neither measurable nor non-measurable) since they are, by definition, simple cysts.

- 'Cystic lesions' thought to represent cystic metastases can be considered as measurable lesions, if they meet the definition of measurability described above. However, if non-cystic lesions are present in the same patient, these are preferred for selection as target lesions.

- Target lesions

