## APPENDIX C-2: PTCL RESPONSE CRITERIA

Response	Site	CT-Based Response	PET-CT Based Response
Complete Response		Complete radiologic response (all of the following)	Complete metabolic response (even with a persistent mass)
	Lymph nodes and extralymphatic sites	
Target nodes/nodal masses must regress to <math>\leq 1.5</math> cm in longest diameter.
 
No extralymphatic sites of disease.
	
Score <math>\leq 3^*</math> with or without a residual mass on 5-point scale†.
 
It is recognized that in Waldeyer's ring or extranodal sites with high physiologic uptake or with activation within spleen or marrow (e.g., with chemotherapy or myeloid colony-stimulating factors), uptake may be greater than normal mediastinum and/or liver. In this circumstance, complete metabolic response may be inferred if uptake at sites of initial involvement is no greater than surrounding normal tissue even if the tissue has high physiologic uptake.

	Nonmeasured lesion	Absent	Not applicable
	Organ enlargement	Rgress to normal	Not applicable
	New lesions	None	None
	Bone marrow	Normal by morphology; if determinate, IHC negative	No evidence of FDG-avid disease in marrow
Partial Response		Partial remission (all of the following)	Partial metabolic response
	Lymph nodes and extralymphatic sites	
<math>\geq 50\%</math> decrease in SPD of up to 6 target measurable nodes and extranodal sites
 
When a lesion is too small to measure on CT, assign 5 mm X 5 mm as the default value
 
When no longer visible, 0 X 0 mm
 
For a node <math>> 5</math> mm X 5 mm, but smaller than normal, use actual measurement for calculation
	
Score 4 or 5† with reduced uptake compared with baseline and residual mass(es) of any size
 
At interim, these findings suggest responding disease
 
At end of treatment, these findings indicate residual disease

Response	Site	CT-Based Response	PET-CT Based Response
	Nonmeasured lesion	Absent/normal, regressed, but no increase	Not applicable
	Organ enlargement	Spleen must have regressed by > 50% in length beyond normal	Not applicable
	New lesions	None	None

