	Bone marrow	Not applicable	Residual uptake higher than uptake in normal marrow but reduced compared with baseline (diffuse uptake compatible with reactive changes from chemotherapy allowed). If there are persistent focal changes in the marrow in the context of a nodal response, consideration should be given to further evaluation with MRI or biopsy or an interval scan
No response or stable disease		Stable disease	No metabolic response
	Target nodes/nodal masses, extranodal lesions	< 50% decrease from baseline in SPD of up to 6 dominant, measurable nodes and extranodal sites; no criteria for progressive disease are met	Score 4 or 5† with no significant change in FDG uptake from baseline at interim or end of treatment
	Nonmeasured lesion	No increase consistent with progression	Not applicable
	Organ enlargement	No increase consistent with progression	Not applicable
	New lesions	None	None
	Bone marrow	Not applicable	No change from baseline
Progressive disease		Progressive disease requires at least 1 of the following	Progressive metabolic disease
	Individual target nodes/nodal masses	PPD progression:	Score 4 or 5 with an increase in intensity of uptake from baseline and/or
	Extranodal lesions	An individual node/lesion must be abnormal with: Longest diameter (LDi) > 1.5 cm and Increase by ≥ 50% from PPD nadir and	New FDG-avid foci consistent with lymphoma at interim OR • End-of-treatment assessment

Response	Site	CT-Based Response	PET-CT Based Response
		An increase in LD i or smallest diameter (SD i ) from nadir 0.5 cm for lesions $\leq$ 2 cm 1.0 cm for lesions $>$ 2 cm In the setting of splenomegaly, the splenic length must increase by $>$ 50% of the extent of its prior increase beyond baseline (e.g., a 15-cm spleen must increase to 16 cm). If no prior splenomegaly, must increase by at least 2 cm from baseline New or recurrent splenomegaly	
	Nonmeasured lesion	New or clear progression of preexisting nonmeasured lesions	None

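### The nodal entry limit and the CT complete-response limit both include 1.5 cm, and Appendix C-1 measures nodes on a different axis from both (minor)

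*Combined protocol and SAP*

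**What the plan says.** **Entry.** Section 3.1 item 8 defines measurable disease by CT, MRI or PET "with at least one nodal site of disease which is 1.5 cm in longest dimension". The nodal limit carries no comparator. The only workable reading is 1.5 cm or more, so 1.5 cm itself qualifies.

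**Response.** In Appendix C-2 the CT route to CR is headed "Complete radiologic response (all of the following". Its nodal line begins "Target nodes/nodal masses must regress to" and sets the limit at 1.5 cm or less in longest diameter. The same column also requires no extralymphatic disease, no remaining nonmeasured lesions, organs of normal size, no new lesions and a normal marrow. Partial response (PR) on CT needs at least a 50% fall in the sum of the products of perpendicular diameters. The progression row starts "An individual node/lesion must be abnormal with: Longest diameter (LDi) > 1.5 cm and".

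**Measurement.** Appendix C-1, Disease Parameters, makes a lymph node measurable at 15 mm or more "in short axis when assessed by CT scan", and adds: "At baseline and in follow-up, only the short axis will be measured and followed". Nodes of 10 to under 15 mm in short axis are non-measurable.

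**Schedule and use.** Note z of Table 10.0 says of PET after screening: "Subsequent PET scans will not be needed until the EOT visit or disease progression, whichever comes first". Table 11.3 defines the overall response rate as CR or PR. Section 12.1.2 tests 10% against 30%, suspends accrual at 0 responses in 7, and rejects the null at 4 or more in 18.

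**The concern.** An entry limit should lie outside the range that the response criteria count as cleared disease. Here the two limits meet at 1.5 cm on the same dimension. The protocol's own progression row does not treat a node of that size as abnormal, so a node can count as qualifying disease at entry and as normal-sized in the response table.

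No other rule reliably catches such a case. PET is not required at the scheduled on-treatment assessments, so these are read on CT. Section 12.5 refers to confirmed responses but does not define confirmation, and a repeat scan of a stable 14 mm node would again fall within the CR limit.

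The design is sensitive to single responses. Four are enough for a positive result, and one in Stage 1 removes the only futility stop. A false CR would also enter the CR rate, a secondary endpoint.

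**Working it through.** **1. The plan's own design.** Inputs from Section 12.1.2: p0 = 0.10, p1 = 0.30, n1 = 7, stop at 0, N = 18, reject at 4 or more.

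P(reject | p) = P(Bin(18,p) ≥ 4) − (1−p)^7 × P(Bin(11,p) ≥ 4)

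- p = 0.10: 0.0982 − 0.4783 × 0.0185 = 0.0893
- p = 0.30: 0.8354 − 0.0824 × 0.4304 = 0.800

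Both stated limits (10% and 80%) are met. A search over two-stage designs with N up to 35 returns this same design as optimal, so the design is reproduced.

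**2. The limits side by side.**

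| Place | Dimension | Limit | Includes 15 mm? |
|---|---|---|---|
| Section 3.1 item 8 (entry) | longest | 1.5 cm, no comparator | yes |
| Appendix C-1 (node measurable) | short axis | ≥ 15 mm | yes |
| Appendix C-2 (CR by CT) | longest | ≤ 1.5 cm | yes |
| Appendix C-2 (abnormal, for progression) | longest | > 1.5 cm | no |

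**3. Which nodes fall in the overlap.** Under item 8 alone, it is any node with a longest dimension of 15 mm. Under item 8 together with C-1, short axis ≥ 15 mm and longest ≤ 15 mm force both to equal 15 mm, so only a round node qualifies. A 15 mm node with a shorter short axis is non-measurable under C-1, and C-2 then requires it to be absent for CR.

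**4. How little change is needed.** Take a 15 × 15 mm node (product 225 mm²) later read as 14 × 14 mm (196 mm²). The fall is 29/225 = 12.9%. PR would require the product to fall to 112.5 mm² or less. The CR size line is met at 14 mm.

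**5. Effect of one certain false responder, true rate 10% in the other 17.**

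- In Stage 1, the futility rule is passed automatically and 3 of 17 are needed: P(Bin(17,0.1) ≥ 3) = 1 − 0.1668 − 0.3150 − 0.2800 = 0.238. The probability of stopping for futility falls from 0.478 to 0.
- In Stage 2, at least 1 of the 7 and at least 3 of the 17 are needed: 0.2382 − 0.4783 × P(Bin(10,0.1) ≥ 3) = 0.2382 − 0.4783 × 0.0702 = 0.205.

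**6. If the share were known.** Let f be the proportion of patients falsely scored CR. The apparent rate under the null is 0.10 + 0.90f. The documents give no f, so these values are assumptions only.

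| Assumed f | Apparent rate | P(declare promising) |
|---|---|---|
| 0 | 0.100 | 0.089 |
| 1% | 0.109 | 0.114 |
| 2% | 0.118 | 0.141 |
| 5% | 0.145 | 0.238 |
| 10% | 0.190 | 0.424 |

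**The case against.** The strongest counter-argument is that this is a single point on a scale and that the text already guards against most of it.

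- **Regression is required.** A reader might infer that an unchanged 1.5 cm node is automatically a CR. The documents do not support that: C-2 says nodes must regress to the limit, and an unchanged node arguably has not regressed. This stands. What remains is a small reading difference, such as 15 mm to 14 mm, which does satisfy the wording.
- **CR is a joint condition.** Any larger node, extranodal disease, enlarged organ, marrow involvement or new lesion blocks it. This also stands, and it confines the problem to patients with nothing but nodes at the boundary.
- **C-1 narrows it further.** Its short-axis rule leaves only near-round nodes, unless a site applies item 8 without C-1. This stands for frequency. But the need to combine two axes to reach that answer is itself a fault. If only the short axis is recorded, neither the longest-diameter CR limit nor the PR product can be calculated.
- **Patients are unlikely to fit.** Item 6 requires failure of at least two systemic therapies, and Section 2.7 describes T-cell disease as aggressive. Disease confined to 15 mm nodes that do not grow should be uncommon. This is a fair judgement, though the documents give no figure.
- **A sign may be missing.** The spleen criterion in the same sentence has a strict comparator and the nodal one has none. If a strict greater-than sign was intended, item 8 has no overlap. The inclusive 15 mm in C-1 weakens this argument, and the wording needs settling either way.
- **A strict limit does not end the noise.** A 16 mm node read as 15 mm would still meet the CR size line. This is true, and it comes from having an absolute CR threshold at all.

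**Conclusion.** The overlap at 1.5 cm is real, and so is the mismatch of axes between Appendix C-1 and Appendix C-2. The practical consequence is narrow. A patient whose only disease is one or more near-round nodes of about 15 mm could be scored CR on a 1 mm reading difference if all the other CR conditions hold.

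The rise from 0.089 to 0.205–0.238 is correct arithmetic for one certain false responder with a true 10% rate in the other 17. A reader might take it as the trial's actual type I error. It is not, because growth, a new lesion or an unchanged reading would each prevent the false CR, and the frequency of such patients is unknown and probably low. The two-stage design itself is sound and reproduces exactly. This is a minor point, worth correcting because the edit is nearly free and the decision turns on four responses.

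**What to change.** 1. In Section 3.1 item 8, state that a qualifying nodal site must be greater than 1.5 cm in longest diameter.
2. Rewrite the nodal definitions in Appendix C-1 to agree with Appendix C-2. C-1 has no longest-diameter line for nodes that could be altered by one symbol. Its short-axis measurability rule, its instruction to follow only the short axis and its short-axis sum must be reconciled with C-2, which uses longest diameter for CR and products of perpendicular diameters for PR. Both diameters need to be recorded at baseline and follow-up.
3. Apply the same strict limit to nodes chosen as targets, so that no eligible target node meets the CR size limit at baseline.

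The cost is a text amendment and a negligible loss of borderline patients. N = 18, alpha 0.089 and power 0.800 are unchanged. The edit does not remove measurement noise for nodes just above 1.5 cm.
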